## Interventions.

**Cognitive Remediation (CR).** CR incorporates a subset of components from Cognitive Enhancement Therapy found to have early benefits on the cognitive deficits of particular interest to the proposed studies and can be conducted more time-efficiently to achieve our specific goals. This abbreviated CR involves 20 hours of neurocognitive training using attention and processing speed training software developed by Ben-Yishay and colleagues. Deficits in Attention are addressed with exercises used to enhance vigilance and rapid decision making, inhibit irrelevant stimuli, and shift attention between auditory and visual modalities. These exercises facilitate reaction time in a temporal mode using auditory cues (The Attention Reaction Conditioner), spatial focusing with visual cues (the

Zero Accuracy Conditioner), and temporal vigilance with auditory and visual cues (Time Estimates). Our experience with over 200 patients with schizophrenia reveals that they successfully progress through these training exercises over the 20 hours of training. For the active control (AC) condition, participants will complete a self-paced knowledge- and vocabulary-based task of the same duration as CR to equate time spent on task, while omitting the cognitive control training aspect that is central to CR.

**Transcranial Direct Current Stimulation (tDCS).** tDCS is a low-cost, portable method that is well-tolerated by participants. The polarity of the current and the location of stimulating electrodes is an important factor that influences its effects on neural activity, with positive polarization (anodal) at the scalp inducing excitation of the underlying cortex, and negative polarization (cathodal) at the scalp resulting in the opposite effect. Functionally, cathodal tDCS suppresses while anodal stimulation facilitates cortical excitability. Modeling studies suggest that layer IV and V pyramidal cells are most affected by tDCS. In PFC, these cells receive direct and indirect regulatory signals from the striatal dopaminergic system, and striatal modulation of prefrontal pyramidal cells has been linked to cognitive control. We believe right inferior frontal gyrus to be the prime candidate for cognitive control enhancement with tDCS, given recent published results showing that greater activation in the right IFG during a standard Stroop task, but not striatum, was associated with greater reduction in cotinine levels. Participants across the 4 conditions will be assigned to a group involving either active (2.0 mA) or sham (0.1 mA) tDCS, with anode electrode placement over the right IFG and cathode electrode placement over the left bicep. tDCS will be administered the first thirty minutes of each of the 10 2-hour CR sessions. During tDCS, patients will be monitored for possible negative side effects.

## Measures.

### **Cognitive Control:**

**MATRICS Clinical Consensus Battery (MCCB).** An abbreviated MCCB will be completed before and after CR + tDCS. Subscales include: Attention: The Continuous Performance Test (CPT), the Continuous Performance Test—Identical Pairs (CPT-IP), and the A-X Continuous Performance Test (AX-CPT). Working memory: N-Back digit sequencing from the BACS, Spatial span from the Wechsler Memory Scale, 3rd ed. (WMS-III), Letter-number sequencing from the WAIS-III, Spatial delayed response task. Reasoning/problem solving: Block design from the WAIS-III, Tower of London from the BACS, Mazes and Categories from the Neuropsychological Assessment Battery, Penn Conditional Exclusion Test, Sorting test from the Delis-Kaplan Executive Functioning Scale. To reduce practice effects, two forms are available for most measures.

**The Continuous Performance Test (CPT)** is a go/no-go task requiring continuously responding to frequent stimuli, and withholding response to a rare target stimulus. EEG will be recorded this task. The AX-CPT also requires maintaining stimulus items in temporary memory store (respond to the letter 'X' only when it follows the letter 'A'). The AX-CPT can measure *proactive cognitive control* of response inhibition. Additionally, a negative ERP, a contingent negative variation (CNV), and a reduction in beta-band oscillations compared to baseline (event-related desynchronization (ERD)), occur between the alerting stimulus ("A") and target stimulus ("X"). Both are blunted in schizophrenia patients and this proactive control deficit may be part of problematic cognitive coordination in schizophrenia.

### **Smoking-related reactivity.**

**Attentional Bias (Reaction time and ERPs)** Participants will be seated in front of a computer with a four-button color response box. Four-word lists (two neutral and two smoking-related) of 15 words each, will be presented in a random order with no repeat. For each trial, a cross appears in the center of the screen for 500ms followed by one word from the list in one of the four colors. Participants respond by pressing the color button that matches the color in which the word appears. Reaction time to respond to each word is recorded within the nearest ms. These procedures are similar to those used

in a past modified-stroop test with smokers. We will also examine EEG correlates of smoking reactivity. In past studies, smokers have increased electrophysiological responses to smoking compared to neutral images, such that their N200 and P300 ERPs are larger in response to smoking stimuli. We will assess this response before and after CR + tDCS to examine neural correlates of attentional bias related to increased N200 and P300 in smokers.

**Cue-Induced craving and smoking topography.** Participants' reactivity to smoking-related cues will also be assessed at Baseline and Week 4 Assessments. To equate time to last cigarette, participants will light a cigarette and smoke as much or as little as they like prior to each the testing session. Cue reactivity testing is computer automated. Following a practice trial, the participant will be viewed by the experimenter on a monitor outside of the subject room to verify compliance with instructions (sit back, focus on pictures, and fill out ratings), which appear on the screen. Four angles of each pictorial cue will be presented for 4 smoking and 4 nonsmoking picture trials with self-report ratings in between. Each cue trial will end with a computer prompt for subjects to complete post-trial craving ratings on a 0-100 scale (4-item Questionnaire on Smoking Urges) After the ratings are filled out for the last cue-reactivity trial, a screen will appear informing subjects that when the pictures return they may smoke as much or as little as they like. They will then complete a 10-minute ad lib smoking / cue-viewing period during which all smoking will occur through a CReSS cigarette holder, allowing for topographical assessment of latency to light, puff volume, and number of puffs.

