## Data Analysis

Prior to hypothesis testing, descriptive statistics and graphic displays will identify outliers and missing data and guide the use of transformations and appropriate tests. Correlation and principal component analysis will identify any outcomes reflecting the same underlying construct, and representative measures will be selected if necessary. We will use 2x2 ANOVA to assess the effects of tDCS (vs sham) and CR (vs AC) on pre-post change scores for all dependent variables. Should baseline differences be identified, post-training scores will be used as dependent variables, and baseline (pre-training) scores will be included as covariates in the analysis.

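### Latency to light is censored at 10 minutes because participants need not light, yet the plan gives non-lighters no value and analyses latency by change-score ANOVA

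*Combined protocol and SAP*

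**What the plan says.** The paragraph on cue-induced craving and smoking topography (under Smoking-related reactivity) tells participants that "when the pictures return they may smoke as much or as little as they like". The window is fixed: "They will then complete a 10-minute ad lib smoking / cue-viewing period". Nothing there obliges anyone to light. To equate time since the last cigarette, "participants will light a cigarette and smoke as much or as little as they like prior to each the testing session". Smoking in the window is through a CReSS holder, "allowing for topographical assessment of latency to light, puff volume, and number of puffs". Whether puff volume means the total over the period or the mean per puff is not stated.

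Study Objectives makes these three measures the Aim 3 outcomes, related within the CR + tDCS group (20 planned) to changes in cognitive control and smoking reactivity.

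The Data Analysis section gives one method for everything: "We will use 2x2 ANOVA to assess the effects of tDCS (vs sham) and CR (vs AC) on pre-post change scores for all dependent variables". If baseline differences appear, "post-training scores will be used as dependent variables, and baseline (pre-training) scores will be included as covariates in the analysis". On irregular data it says that "descriptive statistics and graphic displays will identify outliers and missing data and guide the use of transformations and appropriate tests". No section says what latency is recorded for a participant who does not light.

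**The concern.** Latency to light is a time to event observed for at most 600 s. A participant who does not light has a right-censored time: the value is unknown, but it is known to be longer than that of everyone who lit. A change score needs a number at both visits and the baseline-adjusted alternative needs the same two numbers, so without a scoring rule ordinary ANOVA software omits the person.

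The omission then depends on the outcome itself. If training delays or prevents lighting, which is the direction the trial hypothesises, more people are lost where the effect is larger, and the longest latencies are the ones removed. Replacing dropouts (Procedures and protocol) does not help, because a person who attends both tests and does not light is not a dropout. If the rule is instead settled after the data are seen, the latency result can depend on that choice.

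**Working it through.** **Plan's own figure.** There is none to reproduce. The documents give 20 per group without alpha, power, effect size or SD, and no latency distribution or no-light rate. Every latency input below is an assumption; only the 600 s limit and the group sizes come from the documents.

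**Step 1: what a non-lighter contributes.**

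| Measure | Value if no light | Change score available? |
|---|---|---|
| Number of puffs | 0 | yes |
| Puff volume, 10-minute total | 0 | yes |
| Puff volume, mean per puff | undefined (0/0) | no |
| Latency to light | known only to exceed 600 s | no, unless a rule assigns a value |

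**Step 2: how often.** Assume lognormal latency, with median 60 s at baseline and in controls at Week 4, and treatment multiplying the Week 4 median by 2 or 3. Then P(no light) = 1 - Φ(ln(600/median)/log-SD). At log-SD 1.4:

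- control: ln(10)/1.4 = 1.645, giving 5.0%
- doubled: ln(5)/1.4 = 1.150, giving 12.5%
- tripled: ln(3.33)/1.4 = 0.860, giving 19.5%

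**Step 3: effect on the planned change score.** Log-scale pre-post correlation 0.5 (assumed), 2,000,000 simulated per arm. *Observed-only* is Week 4 minus baseline among those who lit at both visits. *Capped* is min(Week 4, 600) - min(baseline, 600) for everyone. Loss = 1 - observed-only/capped, where d is the difference divided by the pooled SD of change.

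| log-SD | Treatment | Treated not lighting, Week 4 | Difference, observed-only v capped | Loss, seconds | d, observed-only v capped | Loss, d |
|---|---|---|---|---|---|---|
| 0.7 | x2 | 1.1% | 71 v 75 s | 5% | 0.90 v 0.90 | about 0 |
| 0.7 | x3 | 4.3% | 130 v 144 s | 9% | 1.43 v 1.41 | about 0 |
| 1.0 | x2 | 5.4% | 66 v 81 s | 18% | 0.59 v 0.61 | 4% |
| 1.0 | x3 | 11.4% | 113 v 145 s | 22% | 0.94 v 1.00 | 6% |
| 1.4 | x2 | 12.5% | 53 v 78 s | 32% | 0.38 v 0.42 | 11% |
| 1.4 | x3 | 19.5% | 87 v 133 s | 34% | 0.61 v 0.70 | 13% |

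**Step 4: power for a main effect** (40 v 40, two-sided 0.05 assumed, latency doubled). As log-SD falls from 1.4 to 1.0, power rises from about 35% to 72% observed-only, 47% to 78% capped, and 56% to 84% for a rank test on capped Week 4 latency. At log-SD 0.7 all three are about 99%. The step from observed-only to capped is the cost of losing non-lighters; the further gain from ranks comes from using a method suited to a skewed, capped variable.

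**Step 5: the extreme case.** Suppose treatment works only by making a share q of one arm not light, with others unchanged (median 60 s, log-SD 0.8). Mean latency is about 60 x exp(0.8²/2) = 83 s, so the capped difference is about q x (600 - 83): 26 s at 5%, 52 s at 10%, 103 s at 20%, 155 s at 30%. Simulated power with 40 v 40 is about 14%, 37%, 82% and 98%. Observed-only, the difference is about 0 s and rejection about 5% throughout.

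**Step 6: Aim 3 headcount.** Of 20 in CR + tDCS, Week 4 non-lighting would remove 20 x 0.011 = 0.2 (log-SD 0.7, doubled) up to 20 x 0.195 = 3.9 (log-SD 1.4, tripled).

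**The case against.** The strongest reply is that the plan does not exclude anyone. A reader might infer from the change-score ANOVA that non-lighters are to be dropped; the documents do not say so, and assigning 600 s would be equally compatible with them. That is correct: loss is what happens by default, not a stated rule. The Data Analysis section also leaves room for transformations and other suitable tests. That stands too, but it is a choice guided by the data and it gives a non-lighter no score.

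A reader might also infer that those lost are the best responders. The documents do not support this. Everyone lights a cigarette before the session, so not lighting may reflect satiation, and it can occur at baseline or in any arm. The pull toward zero follows only if treatment influences lighting.

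A third tempting reading is that all three topography outcomes are compromised. Puff count and total volume are validly 0; only latency is clearly affected, and puff volume only if it is a per-puff mean.

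On size, comparing Week 4 latency alone at log-SD 1.4 would suggest that 41-43% of the difference in seconds is lost. That ignores the planned change score and rests on one spread; with change scores and smaller spreads the loss is lower. Finally, Aim 3 is a within-group association, whereas Steps 3 to 5 concern between-arm differences. The arm comparison is still planned, since the ANOVA covers all dependent variables, but for the association itself only the headcount has been worked out.

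**Conclusion.** The point holds as a gap with a concrete remedy. A change-score ANOVA, or a baseline-adjusted post score, suits a time censored at 600 s poorly, and the plan supplies no value for the people who are censored. The size cannot be fixed from the documents. It is nil if everyone lights. Under the assumptions in Step 3 it is about 5-34% of the difference in seconds, but only about 0-13% of the standardised effect. It reaches the whole effect if treatment acts solely through not lighting. In Aim 3 it costs from almost no one to about 4 of 20. It warrants correction before analysis; it does not show that the latency result will be wrong.

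**What to change.** Add to the Data Analysis section:

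- **Scoring.** Every attended test is scored. No light within 10 minutes means latency 600 s flagged as censored, puffs 0, and total puff volume 0. Only an unattended or technically failed test is missing.
- **Puff volume.** Define it as the total over the 10 minutes.
- **Latency, arm comparison.** Keep the 2x2 factors and their interaction. Use either a rank-based analysis of Week 4 latency with baseline latency as covariate, or a Cox model for time to light censored at 600 s with baseline adjustment.
- **Latency, Aim 3.** Use a rank correlation within the CR + tDCS group, so that non-lighters stay in at the top tied rank.
- **Reporting.** Give the number of non-lighters by arm and visit, so that non-lighting already present at baseline can be seen.

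The cost is SAP wording and a little more analysis work; no new data, visits or participants are needed. The downside is that a mean latency containing values at the ceiling is less directly interpretable, which is why the test should rest on ranks or time to event.

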## Eligibility Criteria

### Inclusion Criteria:

1. Between the ages of 18 & 65.
2. Currently meets DSM-5 criteria for Schizophrenia, Schizoaffective Disorder, Schizophreniform Disorder, or Delusional Disorder.
3. Ability to provide written informed consent
4. Smoke  $\geq$  7 cigarettes per day
5. Expired breath CO  $\geq$  10 ppm at screening
6. Stable medication regimen for  $\geq$  4 weeks (If on more than one psychotropic medication, main antipsychotic will be considered for stability)

### Exclusion Criteria:

1. Epilepsy or Current Seizure Disorder
2. Alcohol or Substance Dependence past 3 months (caffeine allowed, nicotine is part of inclusion criteria).
3. Pregnant or lactating
4. Psychiatric hospitalization in past 3 months
5. Suicidal and/or aggressive behavior past 3 months
6. Implanted cardiac or brain medical devices

## Data Analysis

Prior to hypothesis testing, descriptive statistics and graphic displays will identify outliers and missing data and guide the use of transformations and appropriate tests. Correlation and principal component analysis will identify any outcomes reflecting the same underlying construct, and representative measures will be selected if necessary. We will use 2x2 ANOVA to assess the effects of tDCS (vs sham) and CR (vs AC) on pre-post change scores for all dependent variables. Should baseline differences be identified, post-training scores will be used as dependent variables, and baseline (pre-training) scores will be included as covariates in the analysis.

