Cognitive enhancement therapy increases cognitive performance in schizophrenia patients, particularly when working memory, processing speed, executive function, and social cognition are targeted. Standard protocols are intensive, taking 18 months to complete, making standard therapy a sub-optimal candidate for smoking cessation. However, the Cognitive Remediation (CR) component of cognitive enhancement therapy focuses specifically on cognitive training and is less intensive and lengthy. When combined with another cognition enhancement method, namely Transcranial Direct Current Stimulation (tDCS), CR may provide a robust and time efficient method of improving cognitive control among patients with schizophrenia. tDCS studies in our lab and others have demonstrated clear enhancement of attention, working memory, and risk aversion using this technique; as well as reductions in craving and amount of smoking. These findings, combined with knowledge of identified cognitive deficits in schizophrenia and the relationship between cognitive function and smoking cessation failure, suggest the potential of CR + tDCS to target cognitive deficits and smoking-related reactivity among smokers with schizophrenia. Specifically, we hypothesize that CR + tDCS will enhance cognitive control, reduce cue-induced craving and attenuate attentional bias (reaction time and ERPs) to smoking stimuli. Further, we will examine if these changes are associated with reductions in actual smoking behavior; and, we will explore the potential of CR + tDCS to increase quit intention and confidence in quitting among smokers with schizophrenia. Our specific aims are as follows:

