## Study Objectives

**Aim 1:** Examine the effectiveness of CR + tDCS to improve behavioral and neurophysiological measures of **cognitive control** among smokers with schizophrenia. Using a 2 X 2 factorial design (n=20 per group) we will examine main and interactive effects of CR and tDCS on multiple measures of cognitive control. Hypothesis: Combined CR + tDCS will result in greater improvement in MATRICS measures of cognitive control, as well as continuous performance task (CPT) relative to the other groups (CR + sham tDCS, AC + tDCS, AC + sham tDCS).

**Aim 2:** Determine the effectiveness of CR + tDCS to attenuate **reactivity to smoking stimuli** among smokers with schizophrenia. Hypothesis: CR + tDCS will lead to greater reductions in cue-induced craving, and improved reaction time and ERP measures of attentional bias relative to the other groups (CR + sham tDCS, AC + tDCS, AC + sham tDCS).

**Aim 3:** Examine if cognitive control enhancement (Aim 1) and/or changes in reactivity to smoking-related stimuli (Aim 2) predict reductions in measures of **actual smoking behavior**. Hypothesis: Enhanced cognitive control and attenuation of reactivity to smoking stimuli will be directly

related to reductions in smoking topography (i.e., Latency to light, puff volume, and number of puffs) within the CR + tDCS group.

**Secondary Aim:** To inform future clinical research, we will also explore whether changes in cognitive control and smoking reactivity measures are associated with changes in **quit intention** and **confidence in quitting** from baseline assessment to end of study by training condition.

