## Study design and methods

Using a 2 x 2 design we examined CR (CR, active control [AC]) X tDCS (active, sham) to enhance cognitive control, reduce cue-induced craving, and attenuate attentional bias measures of reaction time and ERPs to smoking stimuli; and, we determined the impact of these changes on smoking behavior and intent to quit and confidence in quitting among daily smokers with schizophrenia. Participants were assigned to active (2.0 mA) CR + tDCS, CR + sham (0.1 mA) tDCS, active control (AC) + active tDCS, or AC + sham tDCS, each with anode electrode placement over the right inferior frontal gyrus (IFG) and cathode electrode placement over the left bicep. Similar to our previous studies participants received 30 minutes of either active or sham tDCS during each visit, starting at the beginning of the CR training. AC consisted of a self-paced knowledge- and vocabulary-based task in which participants were given sequential multiple-choice questions about factual information at a 6th-grade level. Participants underwent consecutive CR + tDCS sessions, 5 days a week, for 2 weeks. Cognitive control, cue-induced craving and attentional bias (reaction time & ERPs), as well as smoking topography were assessed during Week1 baseline testing and Assessment Week 4.

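### Aims 1 and 2 predict that CR + tDCS outperforms three named groups, but no planned effect tests that comparison

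*Combined protocol and SAP*

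**What the plan says.** Study Objectives, Aim 1, predicts that the combination will do better on the MATRICS battery and on a further task; the comparison reads "as well as continuous performance task (CPT) relative to the other groups (CR + sham tDCS, AC + tDCS, AC + sham tDCS". Aim 2 predicts greater reductions in cue-induced craving and "improved reaction time and ERP measures of attentional bias relative to the other groups", followed by the same three groups.

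Aim 1 also gives the design: "Using a 2 X 2 factorial design (n=20 per group) we will examine main and interactive effects of CR and tDCS". Aim 2 does not mention the interaction.

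The Data Analysis section plans a "2x2 ANOVA to assess the effects of tDCS (vs sham) and CR (vs AC) on pre-post change scores for all dependent variables". If baseline differences are found, "post-training scores will be used as dependent variables, and baseline (pre-training) scores will be included as covariates in the analysis". It does not name the interaction. Neither version of the model comes with a cell contrast, a simple-effect comparison or a rule for deciding when the predicted superiority of the combination has been shown.

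**The concern.** The hypotheses concern one cell of the 2x2 table against the other three. The planned effects are averages over rows and columns and, for Aim 1, a departure from additivity. These are different quantities. If the plan is followed exactly, the central prediction of two of the three main aims has no test.

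Two misreadings then become possible. A significant CR or tDCS main effect could be taken as support for the combination when it does no better than one component. A missing interaction could be taken as failure when the combination is truly the best of the four.

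**Working it through.** **Inputs.** Four groups of 20 (Study Objectives, Aim 1), so 80 in total and error df = 80 - 4 = 76. The documents give no alpha, SD, effect size or power, so there is no figure of the plan's own to reproduce. Assumed for illustration: two-sided 0.05, SD of the analysed score = 1, equal groups, one outcome at a time.

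**Estimands.** Let a, b, c, d be the mean improvements in CR + tDCS, CR + sham, AC + tDCS and AC + sham.

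- CR main effect: (a + b - c - d)/2, SE = sqrt(2/40) = 0.224
- tDCS main effect: (a + c - b - d)/2, same SE
- Interaction: a - b - c + d, SE = sqrt(4/20) = 0.447
- Hypothesis, each-group reading: a - b, a - c and a - d all positive, SE of each = sqrt(2/20) = 0.316
- Hypothesis, average reading: a - (b + c + d)/3 positive, SE = sqrt(1/20 + 1/60) = 0.258

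**Logic, which needs no assumed numbers.** If a = b > c = d, the CR main effect is positive while a - b = 0, so a main effect is not sufficient. If the effects add, a - b - c + d = 0 while a exceeds every other cell, so an interaction is not necessary.

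**Size.** The critical value is t(0.975, 76) = 1.992. Worked example, only CR works at 0.8 SD: the CR main effect is (0.8 + 0.8 - 0 - 0)/2 = 0.8, noncentrality 0.8/0.224 = 3.58, power 94%. The average contrast is 0.8 - 0.8/3 = 0.533, noncentrality 0.533/0.258 = 2.07, power 53%. The all-three column was obtained by simulation (2,000,000 trials per pattern).

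| True means (a, b, c, d) | a beats each group? | CR main effect | Positive interaction | All three contrasts | Average contrast |
|---|---|---|---|---|---|
| Only CR works (0.8, 0.8, 0, 0) | No | 94% | 2.5% | 2.4% | 53% |
| Either component equals the combination (0.8, 0.8, 0.8, 0) | No | 42% | 0.01% | 0.5% | 17% |
| Only the combination works (0.8, 0, 0, 0) | Yes | 42% | 42% | 48% | 86% |
| Effects add (1.6, 0.8, 0.8, 0) | Yes | 94% | 2.5% | 56% | 98% |
| Effects add (1.0, 0.5, 0.5, 0) | Yes | 60% | 2.5% | 19% | 72% |

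Requiring both main effects does not rescue the plan: both are significant in 18% of trials in row 2, where the each-group hypothesis is false, and in 18% in row 3, where it is true. The sign of the interaction separates those two rows, but the plan does not say how it will be read.

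**Error rate of the all-three rule.** If the each-group hypothesis is false, at least one of the three differences is zero or negative. The rule needs that contrast to be significant in the favourable direction, which has probability at most 0.05/2 = 2.5%. This bound is per outcome.

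**Precision.** The 95% CI half-width for one pairwise contrast is 1.992 x 0.316 = 0.63 SD.

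**The case against.** Four points can fairly be made for the plan.

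- **The factorial analysis is coherent and Aim 1 asks for it.** This stands. There is no wrong test or calculation, and Aim 1 does commit to interactive effects. But the interaction answers a question about additivity, and it is not named for Aim 2 or in the Data Analysis section.
- **The text does not say each group.** A reader might infer that the hypotheses require the combination to beat each of the three groups, so that the all-three rule is the only valid test. The documents do not support that. The wording could equally mean the average of the others. The Scientific Background sentence "When combined with another cognition enhancement method, namely Transcranial Direct Current Stimulation (tDCS), CR may provide a robust and time efficient method" explains why the two are paired; it defines no comparison. The gap itself does not depend on the reading, because the contrast is absent under both.
- **The each-group test is weak at this size, while the average contrast is much stronger** (86%, 98% and 72% against 48%, 56% and 19% in the last three rows). This also stands, and it is a reason to choose the reading openly. The average contrast has its own limit: it is significant in 53% of trials when only CR works at 0.8 SD, so it cannot show that the combination beats CR alone.
- **Misreporting is only a possibility.** A reader might infer that the sponsor intends to present a main effect as proof of the combination. Nothing in the documents says so; the Data Analysis section describes the effects as tDCS against sham and CR against AC. The problem is that the plan leaves the question open.

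**Conclusion.** The concern holds as an omission: no planned effect tests the Aim 1 and 2 hypotheses, and no rule says when they are met. Confidence in that is high, because it follows from the text and the algebra alone. The percentages are illustrations that rest on the assumed alpha, SD and effect sizes. Which reading is meant, and therefore which contrast is needed, is for the sponsor to state. The matter should be fixed, but the planned model remains usable. Multiplicity across the many outcomes is a separate point, so the 2.5% bound must not be read as trial-wide.

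**What to change.** Keep the factorial model, name the interaction for both aims, and state which reading is meant. From the same fitted model (change-score or baseline-adjusted), estimate CR + tDCS minus CR + sham, minus AC + tDCS and minus AC + sham, each with a 95% CI. State that a main effect alone will not be reported as showing that the combination beats its components. Then add one of the following:

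- **Each group:** claim superiority only if all three contrasts favour the combination at two-sided 0.05. No alpha split across the three is needed, since all must succeed. Treat failure as inconclusive, not as evidence of no added benefit.
- **Average of the others:** test the combination against the mean of the other three groups, and do not describe the result as beating each component.
- **Factorial hypotheses:** restate Aims 1 and 2 as main and interaction effects. This is the smallest change, but it gives up the claim about the named groups.

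The cost is wording and a few contrasts; no new data are needed. The downside is limited power for the each-group claim. For 80% power it would need about 35 per group if only the combination works at 0.8 SD, 31 if effects add at 0.8 + 0.8 SD, and 79 at 0.5 + 0.5 SD. The estimates and intervals therefore matter more than the verdict of the test.

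The Study design and methods section is in the past tense ("Using a 2 x 2 design we examined CR"), while Procedures and protocol is in the future tense. If the data are already unblinded, label the contrasts as not prespecified.
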